5. SAFETY ANALYSES

5.1 ADVERSE EVENTS

5.1.1 Available data

Adverse events (AEs) are coded into SOC and PTs using MedDRA version 26.0. For each AE, start and stop date/times are collected as well as severity National Cancer Institute common toxicity criteria for adverse events [NCI CTCAE] v5.0⁸, a seriousness flag, treatment relatedness, relatedness to procedures, action taken towards the study drug, outcome, and AE of special interest (AESI) category (bleeding events, infections).

5.1.2 Derivation rules

Treatment-emergent adverse events (TEAE) are defined as AEs starting on or after first dose of IMP and up to and including 60 days after latest dose prior to the event. In case of a (partially) missing AE start date/time, the event will be considered as treatment-emergent, unless the available parts of the AE start date/time provide evidence not to do so.

Based on their start date/time, AEs will be allocated to the phase during which they started. Each AE will therefore be reported in only 1 phase. Phases are defined in section 2.2.1, Table 2. In case the AE start date/time is incomplete or missing and the AE could consequently be allocated to more than 1 phase, a worst-case allocation will be done: the AE will be allocated to the treatment phase unless the available parts of the AE start or stop date/time provide evidence for allocating to the screening phase/follow-up phase. AESIs will also be allocated to analysis periods (see section 2.2.1, Table 3). In case the AESI start date/time is incomplete or missing and the AESI could consequently be allocated to more than 1 period, it will be allocated to the first possible period.

Death is not considered an AE in itself but a ‘fatal’ outcome of an SAE.

An AE for which the study drug was discontinued is defined as an AE with action taken ‘drug withdrawn’.

Injection-related reactions (IRRs) will be defined as all AEs with a MedDRA preferred terms that are listed in either:

- MedDRA Hypersensitivity standardised MedDRA queries (SMQ) broad selection
- MedDRA Anaphylactic reaction SMQ broad selection
- MedDRA Extravasation events (injections, infusions and implants) SMQ broad selection, excluding implants

AND occurring within 48 hours of an injection, or within 2 days in case no AE start time is available. In case of partially missing AE start date, the AE will be considered as an IRR, unless the available parts of the AE start date provide evidence it did not occur within 48 hours of an injection.

	Statistical Analysis Plan	
ARGX-113-2004	Final analysis	Final 1.0 of 7NOV2023

Injection site reactions (ISR) will be defined as PTs in the MedDRA high level term of “injection site reactions”, regardless of the time of onset.

Two AESI types will be used: ‘Bleeding events’ as recorded on the AE section of the CRF and ‘Infections’ as defined using the MedDRA system organ class (SOC) ‘Infections and infestations’.

Adverse events of hypersensitivity are defined as AEs with a MedDRA preferred term listed in the MedDRA Hypersensitivity SMQ broad selection.

Anaphylactic adverse events are defined as AEs with a MedDRA preferred term listed in the MedDRA Anaphylactic reaction SMQ broad selection

Treatment relatedness will be dichotomized as follows in tables:

- Treatment related: related, probably related, possibly related, or missing
- Not treatment related: not related, unlikely related

AE onset and duration will be calculated as follows when start and stop dates are fully known

- AE onset day (versus first administration) =
 - AE start date \geq date of first administration: AE start date – date of first study drug administration + 1 day
 - AE start date < date of first administration: AE start date – date of first study drug administration
- AE duration (days) =
 - AE end date – AE start date + 1 day
 - Study discontinuation date – AE start date + 1 day (when the AE start date is fully known but the AE is not resolved at the end of the study)
In this case the duration will be presented as “>x days”.

Event rates per 100 participant years of follow-up (PYFU) is defined as $100 * \frac{\text{number of treatment-emergent events}}{\text{sum of the follow-up time during which an event is considered treatment-emergent of all participants per treatment expressed in years (ie, divided by 365.25)}}$.

5.1.3 Presentation of results

Tables will present TEAEs only. The AEs will be presented for the overall study duration, including AEs during the follow up. Pre-treatment AEs will only be listed.

An overview table will show the number and percentage of participants with at least 1 event and the number of events for the following:

- TEAEs
- Serious TEAEs
- Non serious TEAEs
- Grade ≥ 3 TEAEs
- Fatal TEAEs
- Treatment related TEAEs according to the principal investigator
- Procedures related TEAEs

	Statistical Analysis Plan	
ARGX-113-2004	Final analysis	Final 1.0 of 7NOV2023

- Serious treatment related TEAEs
- TEAEs for which the study was discontinued
- TEAEs for which the study drug was discontinued
- TEAEs for which the study drug was interrupted
- TEAEs of special interest: bleeding events
- TEAEs of special interest: infections
- ISR TEAEs
- IRR TEAEs
- TEAEs of hypersensitivity
- TEAEs of anaphylactic reaction

In addition, the number of events per participant years on study will be added to the overview table.

The overview table will be repeated, overall and by 12-week period (as defined in [Table 3](#)), specifically for ISR events, omitting the records related to TEAEs of special interest and ISR events.

Summary tables by MedDRA SOC and PT will show the number and percentage of participants with at least one event. The table of TEAEs will additionally show the number of events. The table of ISR events will be presented overall and by 12-week period (as defined in [Table 3](#)).

Summary tables by MedDRA SOC and PT will show the number and percentage of participants with at least 1 event. The table of TEAEs will additionally show the number of events.

Separate tables will be prepared for the following TEAEs:

- Serious TEAEs
- Non serious TEAEs
- Grade ≥ 3 TEAEs
- Fatal TEAEs
- Treatment related TEAEs according to the Principal Investigator
- TEAEs related to study procedures
- Serious treatment-related TEAEs
- TEAEs leading to discontinuation from the study
- TEAEs leading to discontinuation of study drug
- TEAEs for which the study drug was interrupted
- TEAEs of special interest: bleeding events
- TEAEs of special interest: infections
- ISR events
- Serious ISR events
- IRR events
- Serious IRR events
- TEAEs of hypersensitivity

	Statistical Analysis Plan	
ARGX-113-2004	Final analysis	Final 1.0 of 7NOV2023

- TEAEs of anaphylactic reaction

Tables on TEAEs, serious TEAEs, hypersensitivity and anaphylactic events will be repeated by ADA and NAb against efgartigimod participant classification and by antibodies against rHuPH20 participant classification.

All AEs, including pre-treatment events will be listed.

5.2 CLINICAL LABORATORY EVALUATION

5.2.1 Available data

Per CTP, the following laboratory parameters are expected:

- Biochemistry: creatinine, creatinine clearance (BSA adjusted), blood urea nitrogen (BUN), alanine aminotransferase (ALT), aspartate aminotransferase (AST), total bilirubin, gamma-glutamyl transferase (GGT), C-reactive protein (CRP), alkaline phosphatase (ALP), lactate dehydrogenase (LDH), uric acid, albumin, potassium, sodium, total calcium, hemoglobin A1c (HbA1c), cholesterol (total cholesterol, high density lipoprotein [HDL], low density lipoprotein [LDL]), triglycerides, apolipoprotein B, lipoprotein A.
- Hematology: hemoglobin, white blood cell (WBC) count with WBC differentials, fibrinogen, von Willebrand factor, D-dimer.
- Urinalysis: color, clarity/appearance, specific gravity, pH, protein, glucose, ketones, blood, bilirubin, urobilinogen, nitrite, leukocyte esterase, and microscopic examination including red blood cell (RBC) count, WBC, casts, crystals, bacteria.

Normal ranges are available as provided by the laboratory.

	Statistical Analysis Plan	
ARGX-113-2004	Final analysis	Final 1.0 of 7NOV2023

5.2.2 *Derivation rules*

The following parameters will be derived:

- Estimated glomerular filtration rate (eGFR) (Chronic Kidney Disease Epidemiology Collaboration [CKD-EPI]) ($\text{mL}/\text{min}/1.73\text{m}^2$) = $141 * \text{minimum}(\text{creatinine} [\text{mg}/\text{dL}] / \text{K}; 1)^\alpha * \text{maximum}(\text{creatinine} [\text{mg}/\text{dL}] / \text{K}; 1)^{-1.209} * 0.993^{\text{age}(\text{years})} * [1.018 \text{ if female}] * [1.159 \text{ if race} = \text{black}]$
where $\text{K} = 0.7$ if female and $\text{K} = 0.9$ if male; $\alpha = -0.329$ if female and $\alpha = -0.411$ if male
- The following abnormality categories will be defined:
 - Low: value < lower limit of normal range
 - Normal: lower limit of normal range \leq value \leq upper limit of normal range
 - High: value > upper limit of normal range

Note:

- Classification will be done in standardized units, using non-imputed values and limits.
- For the worst-case analysis visits, as defined in section 2.2.5, an additional category low + high is defined in case there are both low and high postbaseline values.

Toxicity grades will be computed according to the NCI CTCAE toxicity grading list (version 5.0⁸). The implementation of these toxicity grades for analysis is presented in appendix 9.3. Additional study-specific toxicity gradings will be applied as defined in appendix 9.4. Only the parameters described in appendices 9.3 and 9.4 will be computed, according to the declared limits for each grade.

5.2.3 *Presentation of results*

The statistical analysis will present results in standardized units, except for eGFR, which will be reported in $\text{mL}/\text{min}/1.73 \text{ m}^2$.

Continuous laboratory parameters will be summarized by means of descriptive statistics at each analysis visit. Actual values and changes from baseline will be shown in the same table. Categorical urinalysis results will be listed only. Only central lab (ie, CERBA research) assessments will be considered in the table, except for the worst-case analysis visit, where specific rules hold.

Laboratory abnormalities will be presented as cross-tabulations of the abnormality at each postbaseline analysis visit and at the worst-case analysis visit versus the baseline abnormality. Numbers of participants with treatment-emergent abnormalities (see [Definition of terms](#)) will also be shown. The denominator for the percentage is the total number of participants having data for the parameter per treatment and per analysis visit in the safety analysis set. Both central laboratory and local laboratory assessments will be considered in the table.

Laboratory toxicity grades will be presented as cross-tabulations (shift table) of the toxicity (NCI-CTCAE grades) at each postbaseline analysis visit and at the worst-case analysis visit versus the baseline toxicity. Numbers and cumulative numbers over decreasing toxicity grading of participants with treatment-emergent toxicities

	Statistical Analysis Plan	
ARGX-113-2004	Final analysis	Final 1.0 of 7NOV2023

will also be shown. The denominator for the percentage is the total number of participants having data for the parameter per treatment and per analysis visit in the safety analysis set. Parameters having toxicity grades defined in both directions (hypo and hyper) will be shown by direction. All central laboratory assessments and the subset of local laboratory assessments for which toxicity grades are defined based on local normal ranges only (ie, parameters flagged in appendix 9.3 and 9.4) will be considered in the table. The worst-case analysis visit of a participant will only be considered in the cross-tabulation if the laboratory parameter is flagged in appendix 9.3 or 9.4 or if the parameter is not flagged but all the baseline and postbaseline assessments of the participant are from the central lab.

The tables will only show analysis visits as expected per SoA (including the follow-up phase).

All laboratory data will be listed, but only for participants with any postbaseline abnormality.

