8.3.5. Clinical Safety Laboratory Assessments

- Blood and urine samples for determination of clinical chemistry, hematology, urinalysis, coagulation, thyroid, autoimmune antibody testing, follicle-stimulating hormone (FSH; only for women of non-childbearing potential), viral testing, and tuberculosis QuantiFERON test will be collected and analyzed at a central laboratory as indicated in the SoA (Section 1.3) and Section 10.2. The blood sample for platelet counts and the urine sample for the pregnancy test will be analyzed locally.
- For safety assessments during screening, participants may be rescreened (ie, redoing the full assessments as per SoA, Section 1.3) or retested once (ie, repeating 1 test, see Section 5.4) if still within the screening period.
- On days that IMP is administered, samples for laboratory assessments should be collected before dosing, unless otherwise requested.
- Additional safety samples may be collected if clinically indicated, at the discretion of the investigator.
- For all female participants of childbearing potential, a serum pregnancy test will be performed centrally at screening (on the samples taken for clinical laboratory tests), and a urine pregnancy test will be conducted and analyzed locally at the investigative site at the visits specified in the SoA (Section 1.3).
- Clinical laboratory tests will be reviewed for results of potential clinical significance at all time points throughout the trial, with the exception of albumin and urine total protein (quantitative) values. Albumin and urine total protein (quantitative) values will remain blinded for the trial site. An alert system will be implemented to notify the investigator if there are out-of-range albumin or urine total protein (quantitative) values to allow for appropriate safety follow-up.
- The investigator will evaluate any change in laboratory values. If the investigator determines a laboratory abnormality to be clinically significant, it will be considered as a laboratory AE; however, if the abnormal laboratory value is

consistent with a current diagnosis, it may be documented accordingly without being reported as AE.

- The details of sampling, handling, storage, and transportation of the samples will be described in the laboratory manual.
- The actual sample collection date and time must be entered in the participant's source documents and on the central laboratory assessment eCRF page. For urinalysis samples only the date of collection is to be entered.

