	Statistical Analysis Plan	
ARGX-113-2004	Final analysis	Final 1.0 of 7NOV2023

	counts/mm ³	<LLN-500	<500-200	<200-50	<50
Fibrinogen ^[3]		<1.00-0.75 *LLN	<0.75-0.50 *LLN	<0.50-0.25 *LLN	<0.25 *LLN
International normalized ratio ^[3]		>1.2-1.5 *ULN	>1.5-2.5 *ULN	>2.5 *ULN	-
Lymphocytes (absolute count) low ^[1]	giga/L	<LLN-0.80	<0.80-0.50	<0.50-0.20	<0.20
	counts/mm ³	<LLN-800	<800-500	<500-200	<200
Lymphocytes (absolute count) high	giga/L	-	>4-20	>20	-
	counts/mm ³	-	>4000-20000	>20000	-
Neutrophils (absolute count) ^[1]	giga/L	<LLN-1.5	<1.5-1.0	<1.0-0.5	<0.5
	counts/mm ³	<LLN-1500	<1500-1000	<1000-500	<500
Platelets ^[1]	giga/L	<LLN-75	<75-50	<50-25	<25
	counts/mm ³	<LLN-75000	<75000-50000	<50000-25000	<25000
White blood cells ^[1]	giga/L	<LLN-3	<3-2	<2-1	<1
	counts/mm ³	<LLN-3000	<3000-2000	<2000-1000	<1000

^[1] In case ULN/LLN is higher/lower than the upper/lower limit of grade 1 (or even higher grades), ULN/LLN will be ignored and only the fixed values of CTCAE will be considered. In case ULN/LLN is missing, a grade will only be derived if the value leaves no doubt on which grade is to be assigned.

^[2] Grade definition will also be applied when the fasting conditions into which the sample was drawn have not been declared (e.g. unscheduled samples, unknown), when only (a) sporadic result(s) for the parameter was (were) non-fasting (usually unscheduled samples), and in case of scheduled post-meal samples on a same day (e.g. 4 hours after dose and after a meal).

^[3] Local lab assessments of this lab parameter can be considered in the lab toxicity table.

	Statistical Analysis Plan	
ARGX-113-2004	Final analysis	Final 1.0 of 7NOV2023

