9.4 TOXICITY GRADES THAT ARE NOT COVERED BY CTCAE, v5.0

Table 19: Toxicity Graded that are not Covered by CTCAE, v5.0

PARAMETER	Unit	GRADE 1	GRADE 2	GRADE 3	GRADE 4
Hemoglobin decreased (anemia)	g/L	<LLN – 100	<100 – 80	<80	-
Hemoglobin increased ^[1]	g/L	>ULN – (ULN + 20)	>(ULN + 20) – (ULN + 40)	>(ULN + 40)	-
White blood cell (WBC decreased)	giga/L	<LLN – 3.0	<3.0 – 2.0	<2.0 – 1.0	<1.0
White blood cell (WBC) (leukocytosis)	giga/L	-	-	>100	-
Prothrombin Time (PT) ^[1]		>ULN – 1.5 *ULN	>1.5 *ULN – 2.5 *ULN	>2.5 *ULN	-
BSA adjusted creatinine clearance decreaseddecreased	mL/min/1.73m ²	< LLN – 60	<60 – 30	<30 – 15	<15
Blood urea nitrogen ^[1]		>ULN - ≤1.5 *ULN	>1.5 *ULN - ≤3.0 *ULN	>3.0 *ULN - ≤6.0 *ULN	>6.0 *ULN

^[1] Local lab assessments of this lab parameter can be considered in the lab toxicity table.

	<h3>Statistical Analysis Plan</h3>
ARGX-113-2004	Final analysis
Final 1.0 of 7NOV2023	

Trial Period ^a	Screening	Treatment Period																								End-of-Treatment	Early Discontinuation	Follow-up 1	Follow-up 2	Unscheduled																										
		1 Baseline	2	3	4	5	6	7	8	9	10	11	12	13	14	15	16	17	18	19	20	21	22	23	24																															
Visit																																																								
Trial day	-14 to -1	1	8	15	22	29	36	43	50	57	64	71	78	85	92	99	106	113	120	127	134	141	148	155	162	169																														
Visit window, days																																																								
Pharmacokinetics ^{h,n}		X	X	X	X	X ^o	X ^o	X ^o	X ^o	X ^o	X ^o	X ^o	X ^o	X ^o	X ^o	X ^o	X ^o	X ^o	X ^o	X ^o	X ^o	X ^o	X ^o	X ^o	X ^o	X ^o	X ^p	X	X	X	X	X	X																							
Randomization ^f		X																																																						
IMP administration ^g		X	X	X	X	(<----- qw or q2w administration ----->)																																																		
Caregiver informed consent form ⁱ																																																								
IMP (self-)administration training ^{g,u}																																																								
Collecting information related to hospitalization for ITP management																																																								
Concomitant therapies/procedures ^v																																																								
Adverse events ^v																																																								

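### SAP 5.2.3 drops a participant's worst-case laboratory toxicity grade for unflagged parameters once any value is local, even when the severe value was central

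*SAP*

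**What the plan says.** SAP 5.2.3 (Clinical laboratory evaluation, Presentation of results) builds the toxicity shift table from all central values plus "the subset of local laboratory assessments for which toxicity grades are defined based on local normal ranges only". The parameters concerned are marked by footnote: [3] in appendix 9.3, which reads "Local lab assessments of this lab parameter can be considered in the lab toxicity table", and a footnote with the same wording, numbered [1], in appendix 9.4. Footnote [1] in appendix 9.3 means something else.

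The worst-case visit has its own condition. It "will only be considered in the cross-tabulation if the laboratory parameter is flagged in appendix 9.3 or 9.4". An unflagged parameter gets a worst-case entry only when none of that participant's values, at baseline or afterwards, comes from a local laboratory.

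SAP 2.2.5 defines the worst-case visit more widely: every available postbaseline value counts, unscheduled ones included, and the toxicity worst case is derived per parameter and direction. It names no exception for local laboratories.

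Protocol 8.3.5 makes the central laboratory the default for chemistry and hematology. It adds: "Additional safety samples may be collected if clinically indicated, at the discretion of the investigator". It does not say which laboratory handles those samples. The SAP's list of tables marks 14.3.2.3 (toxicity grades) as top-line and leaves 14.3.2.2 (low/normal/high) unmarked.

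**The concern.** A wish not to mix laboratories can justify leaving out a local value. It does not justify discarding the central values of the same participant. As written, one local result for an unflagged parameter, at baseline or later and normal or not, takes away the worst-case grade even when the central laboratory recorded the severe value.

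The parameters affected matter here. Infection and bleeding are the trial's adverse events of special interest, and neutrophils, lymphocytes and low hemoglobin are the laboratory measures closest to them. If local testing is more common in participants who are unwell, the exclusion depends on the outcome being counted and could differ between arms.

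**Working it through.** **Which parameters are affected.** Reading the footnotes in 9.3 and 9.4:

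- Flagged in 9.3: amylase, ALT, alkaline phosphatase, AST, bilirubin, creatine kinase, creatinine, GGT, lipase, aPTT, fibrinogen, INR. Flagged in 9.4: hemoglobin increased, prothrombin time, blood urea nitrogen.
- Not flagged: the row beginning "Hemoglobin decreased (anemia", neutrophils, lymphocytes, WBC, albumin, potassium, sodium, calcium, magnesium, glucose, cholesterol, triglycerides, CD4 count and creatinine clearance. Platelets are also unflagged, but they are reported as efficacy and I set them aside.

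**What happens to one participant.** Suppose central neutrophils are grade 4 on one occasion and a single local neutrophil count is normal. The parameter is unflagged and not all values are central, so there is no worst-case entry. Under 2.2.5 the entry would be grade 4. The two sections cannot both be applied.

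**What remains elsewhere in the table.** Central values stay in the by-visit rows. SAP 2.2.4 allocates unscheduled values to windows too, but keeps only the value closest to the target day. A severe central value may therefore appear in a by-visit row or may lose to another value in its window. Only the worst-case row is meant to consider every value.

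**Can local values be graded?** Grades 3 and 4 of the main unflagged parameters rest on fixed limits: hemoglobin below 80 g/L (grade 3), neutrophils below 1.0 giga/L (grade 3 or 4), potassium below 3.0 or above 6.0 mmol/L (grade 3 or 4). A normal range is needed mainly for grade 1, and for grade 2 of low potassium, which starts at the lower limit of normal.

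**Size.** The documents give no figure to reproduce, so this is an illustration. Assumed inputs: f, the share of participants with any local value; p = 5%, the severe-grade rate in central-only participants; r, the relative rate in those with a local value. From the documents: up to 180 + 39 = 219 randomized 2:1, so 219 × 2/3 = 146 on efgartigimod.

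- Everyone kept: (1 − f)p + f·r·p
- Shown, if excluded participants leave the denominator: p
- Shown, if they stay in it: (1 − f)p

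| f | Everyone kept, r = 0.5 | r = 1 | r = 4 | Shown, out of denominator | Shown, in denominator |
|---|---|---|---|---|---|
| 2% | 4.95% | 5.0% | 5.3% | 5.0% | 4.9% |
| 10% | 4.75% | 5.0% | 6.5% | 5.0% | 4.5% |
| 20% | 4.5% | 5.0% | 8.0% | 5.0% | 4.0% |

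For f = 10% and r = 4: 0.9 × 5% + 0.1 × 20% = 6.5%, or 9.5 of 146 participants. The table would show 146 × 0.9 × 5% = 6.6 of 131.

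The count falls in every row. With excluded participants out of the denominator, the percentage is understated if r > 1, unchanged at r = 1 and slightly overstated if r < 1. With them left in, it is understated for any r above zero. SAP 5.2.3 bases the denominator on participants with data for the parameter at that visit, which does not settle the choice for the worst-case row.

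**The case against.** The strongest reply is that this is one row of a descriptive safety table, with other safeguards around it. Clinically significant laboratory abnormalities are reported as AEs and graded by CTCAE. AEs of grade 3 or more, bleeding and infections each have a top-line table (14.3.1.5, 14.3.1.13, 14.3.1.14). Table 14.3.2.2 uses local values, and Listing 16.2.8.1 shows the data of participants with abnormal values. All of that stands, but none of it gives the laboratory-graded worst-case count: the AE tables depend on the investigator's judgment of significance, 14.3.2.2 carries no grades, and a listing is not a count.

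A second reply is that keeping only central values would also mislead, since a local grade 4 beside a central grade 1 would show as grade 1. That is a fair point against a central-only remedy. It is met by also admitting local values that fixed limits can grade.

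A third is that hemoglobin may count as flagged because its high direction is. Reading by direction fits better: 2.2.5 derives the worst case per direction, the flag is set row by row, and the low direction is not graded on normal ranges alone. If hemoglobin were taken as flagged, the other parameters would remain.

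A reader might infer more than the documents support:

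- That affected participants leave the whole table. They leave only the worst-case row, for that parameter.
- That local values come mainly from ill or bleeding participants. This is plausible but not stated. The only route to local testing the protocol describes for these parameters is the COVID-19 appendix, which calls it exceptional.
- That the SAP already allows local hemoglobin to be graded because "a grade will only be derived if the value leaves no doubt on which grade is to be assigned". That clause stands in 9.3 and concerns a missing normal limit; low hemoglobin is graded in 9.4.

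**Conclusion.** The point holds as a defect in the tabulation rule. SAP 5.2.3 contradicts 2.2.5 and can remove a centrally measured severe grade from the worst-case row of a top-line table because of an unrelated local value. No other planned table restores that count.

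The direction is certain for the count, which can only be lowered. For the percentage it depends on the denominator and on the relative risk in participants with local values, neither of which the documents settle. At the assumed 5% base rate with 10% having a local value, the figure with everyone kept is 4.75% to 6.5%, against 5.0% shown with excluded participants out of the denominator.

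A reader might expect a much larger distortion. Assuming 2% severe grades in central-only participants and 20% to 40% in the others, 10% local use gives 0.9 × 2% + 0.1 × 20% = 3.8% up to 0.9 × 2% + 0.1 × 40% = 5.8%, against 2.0% shown. That needs a 10- to 20-fold risk, for which the documents give no basis. The primary and key secondary analyses are not affected.

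**What to change.** Replace the all-central condition in SAP 5.2.3 with a rule in four parts:

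1. A local value never removes a participant's worst case from central values.
2. Local values, converted to standardized units, enter the worst case when fixed limits set their grade without a normal range (for example hemoglobin below 80 g/L). State this for both 9.3 and 9.4.
3. Leave out only local values whose grade cannot be determined. For the main parameters named above, these cannot be grade 3 or 4.
4. Footnote the number of participants with such values, per parameter and arm.

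Reconcile the text with 2.2.5, state the denominator of the worst-case row, and record the change in SAP 6.3.

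The cost is a short SAP amendment, some unit conversion and minor programming. No new data are needed.
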